The study will collect data on patient outcomes prior to the introduction of the alert for a maximum of five years and up to three years post the duration of the alert. We may have to use shorter time periods for certain Trusts.

Sampling Strategy

We have identified five digitally mature NHS Trusts in England, each operating a digital sepsis alerts. In addition, we are working with a Trust in Wales which is still paper based.

Methods of Data Collection

A detailed data specification and data dictionary will be compiled, with associated SNOMED codes for each observation. All data items are routinely collected and recorded in patient electronic records. All data will be de-identified. We will use the NIHR-HIC data infrastructure to enable data transfer. Please see Section for more details.

Outcomes

The primary outcome will be **all-cause in-hospital mortality within 30 days**. Secondary outcomes (including process measures):

- Transfer to ICU
- Length of stay
- Readmission within 30 days
- Administration of IV antibiotics
- Venous blood tests including lactate and white blood cell count
- Blood cultures ordered

The primary reason for the introduction of EWS systems, including digital alerts, is to prevent avoidable clinical deterioration. Mortality is a key measure of clinical deterioration and the majority of EWS have been validated by assessing their ability to predict mortality. Mortality is recorded in hospital patient records and reported as part of the Secondary Users Service (SUS). It is therefore a reliable and commonly used measure of clinical deterioration. Transfer to ICU is often used as an additional measure of clinical deterioration and is available in EHRs.

Length of stay and readmission within 30 days are important indicators of patient experience and are key targets for hospitals. The aim of early recognition of sepsis is to enable prompt and appropriate treatment. We will therefore assess whether the introduction of digital alerts has impacted on appropriate treatment.

Assessment of unintended consequences

Based on discussion in the Sepsis Big Room clinical teams are concerned about potential increases in unnecessary treatment as an unintended consequence of digital alerting. We will consider four potential measures of unintended consequences:

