For the primary analysis we will identify patient hospital encounters where the alert was active and visible to clinicians and use EHRs to identify a cohort of patients who have the same clinical characteristics as the alerting patients, based on routinely recorded vital signs or alerting software. These will act as a control group. Statistical analysis plans will be dependent on the implementation approach in individual Trusts. In line with the approaches recommended in the MRC guidance, methods to be included are those where the factors which determine the exposure can be measured: matching; regression adjustment; and propensity score approaches. We will also utilise methods which are best suited for adjusting for pre-implementation trends including interrupted time series. All analyses will be adjusted for clustering of patients within wards or Trust sites.

Secondary analysis

We will use a controlled multilevel interrupted time series regression to examine trends in mortality for patients with codes defined as 'suspicion of sepsis' and a more robust definition of sepsis. utilise this method to examine unintended consequences identified above.

Sensitivity analysis

We will consider mortality following an A&E attendance for stroke and/or trauma as an unrelated outcome in a sensitivity analysis. Although these patients may trigger an alert, we would not expect their treatment to be different after the introduction of the alert as they are likely to be identified rapidly on arrival. This will enable an assessment of the specificity of effect. This will be included in primary and secondary analysis. These conditions will be included as controls in controlled interrupted time series.

Study Sequence and Duration

Data extraction will commence in March 2022 and be completed by May 2022. Analysis will be completed by December 2022.

7.3 WorkStream 3 – To explore the views and experiences of healthcare professionals and patients/carers on the use of digital sepsis alert systems in hospitals.

Methodology

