1.1 Background/rationale

To improve care for patients with sepsis, comply with national financial incentive programmes, and make best use of the introduction of electronic health records hospitals in England have introduced digital sepsis alerts. A variety of algorithms have been used, with different workflows and with different implementation strategies.

A variety of studies have demonstrated that digital sepsis alerts, and more general deteriorating early warning scores such as NEWS2, have high predictive power for mortality.[1] A small number of studies have shown that introducing digital alerts to identify patients at risk of deterioration have had an impact on patient outcomes.[2-3]

Although randomised control trials are considered the gold standard for evidence, digital alerts have generally been introduced across hospitals without randomisation or phased across the hospital. In ICHT sepsis alerts were introduced in a phased approach and we used a propensity score based causal inference method (inverse probability of treatment weighting), common in the analysis of natural experiments, to emulate as much as possible a RCT using real world healthcare data. In ICHT the introduction of digital sepsis alerts was associated with a 23% lower risk of death within 30 days.[4]

In this study we aim to analyse the impact of the introduction digital alerts across five NHS Trusts. With the exception of ICHT the introduction of alerts was part of the introduction of electronic health records (EHR). This presents challenges, for example:

- Data availability prior to the introduction of EHRs is limited to data routinely collected for administrative purposes. This includes admission, discharge and formal diagnosis information, but excludes detailed microbiology information and detailed patient treatment information such as the administration of antibiotics.
- The impact of the alerts on patient outcomes will be confounded by the introduction of EHRs, a major change in the hospital system.

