Length of stay - length of stay, measured in hours, was determined from the date and time of admission and discharge recorded in the patient record. For this descriptive study we will quantify length of stay for patients who are discharged alive.

Mortality – mortality was based on discharge destination recorded. For the purposes of this study only inhospital mortality was available for all NHS trusts.

Missing data

Patient admissions will not be excluded if patient data is missing, an additional category of missing will be included for age, gender, ethnicity and deprivation. As part of quality checks we will confirm whether there are any patterns in missing data.

Statistical methods

(a) Describe all statistical methods, including those used to control for confounding

Descriptive analysis

We will describe trends in patient mix over time using graphical methods, we will use time series to determine if there were changes in patient mix, including sub-groups of patients, patients with SoS and falls patients.

We will use break point approaches to identify potential key points in time where changes occurred. This will aid in interpretation of results.

Comparative analysis

We will use interrupted time series with a control, adjusted for patient case mix and season. Each Trust will be modelled separately as the introduction of sepsis alerts and electronic health records is different for each Trust. Comparisons will be made between the change in slope and step change in counts.

(b) Describe any methods which will be used to examine subgroups and interactions

Within each model we will separately consider subgroups when we perform our analysis. We will consider a priori interactions.

(c) Explain how missing data will addressed

Missing data will be included as a category on its own for factors such as ethnicity and deprivation. We will inspect data to identify periods of missing data, and consider imputation.

ICD-10 Code	ICD-10 Description
1850	Oesophageal varices with bleeding
K226	Gastro-oesophageal laceration - haemorrhage syndrome K228 Other specified diseases of oesophagus
K250	Gastric ulcer, acute with haemorrhage
K252	Gastric ulcer, acute with both haemorrhage and perforation
K254	Gastric ulcer, chronic or unspecified with haemorrhage K256 Chronic or unspecified Gastric ulcer with both haemorrage and perforation
K260	K260 Duodenal ulcer, acute with haemorrhage
K262	K262 Duodenal ulcer, acute with both haemorrhage and perforation

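### Section 7.2 and the appendix do not agree on the primary analysis of 30-day in-hospital mortality, and the controls that Section 7.2 describes appear available before the alert only at ICHT

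*Protocol*

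**What the plan says.** **Protocol, Section 7.2, Primary analysis.** The exposed group is defined first: "For the primary analysis we will identify patient hospital encounters where the alert was active and visible to clinicians". The controls come next: the team will "use EHRs to identify a cohort of patients who have the same clinical characteristics as the alerting patients, based on routinely recorded vital signs", and the full phrase offers a second route, "based on routinely recorded vital signs or alerting software". The methods named are matching, regression adjustment and propensity scores. The same paragraph says that plans will depend on how each Trust introduced its alert, and adds ITS among the methods for handling earlier trends.

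**Protocol, Section 7.2, Secondary analysis.** "We will use a controlled multilevel interrupted time series regression to examine trends in mortality for patients with codes" on the SoS list, and for a stricter sepsis definition.

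**Protocol, Section 10.** For Workstream 2 the reader is sent to Appendix 1 for the detailed statistical plans.

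**Appendix, impact study.** The method is ITS with a control. The intervention group is patients with an SoS code at discharge, and the primary outcome is in-hospital mortality within 30 days. On model structure: "Each Trust will be modelled separately as the introduction of sepsis alerts and electronic health records is different for each Trust". No matched or propensity analysis is planned; inverse probability weighting appears only in the account of earlier work at ICHT.

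**Data description.** Appendix, impact study, 1.1: "With the exception of ICHT the introduction of alerts was part of the introduction of electronic health records (EHR"), and "Data availability prior to the introduction of EHRs is limited to data routinely collected for administrative purposes". Section 7.2, Sampling Strategy, on the sixth Trust: "we are working with a Trust in Wales which is still paper based".

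**The concern.** A reader who wants to know which analysis answers the main question gets two replies. Section 7.2 points to a patient-level comparison of alerting encounters with controls. The appendix points to a time series in coded patients. These differ in method and also in population: encounters that alert, or would have alerted, against everyone discharged with an SoS code, whether or not they alerted. They estimate different effects on the same endpoint.

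The analysis labelled primary also seems to lack the data it needs in most Trusts. It requires patients who had the same observations but were not exposed to a visible alert, and the natural source is the period before the alert was switched on.

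What is at stake is interpretation. If both analyses are run and disagree, the protocol does not say which one counts. The matched approach is most clearly feasible at ICHT, where the appendix already reports a 23% lower risk of death within 30 days from a propensity-weighted analysis. With the order unsettled, a result of that kind could be presented as primary ahead of the multi-Trust time series. The text does not plan for this, but does not prevent it.

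**Working it through.** The protocol gives no sample size, power or significance level for the impact study, so there is no stated figure to reproduce. The check is a comparison of sections and a count of Trusts.

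**Step 1: is the primary analysis the same in both places?**

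| | Section 7.2, primary | Section 7.2, secondary | Appendix, impact study |
|---|---|---|---|
| Population | Alerting encounters and similar controls | SoS-coded patients (and a stricter sepsis definition) | SoS-coded patients |
| Method | Matching, regression adjustment, propensity scores; ITS also named | Controlled multilevel ITS | Controlled ITS, one model per Trust |
| Outcome | Study primary outcome: 30-day in-hospital mortality | Mortality trends | 30-day in-hospital mortality as primary outcome |

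The appendix column matches the secondary column in population and in basic method. The cohort comparison in the primary column has no counterpart in the appendix.

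**Step 2: where could pre-alert controls with electronic vital signs come from?**

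- Trusts in the impact study: 6 (five English, one Welsh).
- English Trusts where the alert came in as part of the EHR: 5 − 1 (ICHT) = 4. The appendix paragraph on bias also counts four of six Trusts with simultaneous introduction. Its sentence says alerts arrived at the same time as alerts; the sense must be EHR and alert together.
- In those four Trusts, data from before the EHR, and so from before the alert, are administrative only.
- Paper-based Trusts: 1 (Wales).
- Remaining: 6 − 4 − 1 = 1, namely ICHT, where the alert was phased in.

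The appendix does not list vital signs among the missing pre-EHR items. Their absence follows from its statement that the data are limited to administrative records.

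**Step 3: could controls come from elsewhere?**
Section 7.2 does not require controls to pre-date the alert, and it allows them to be found by alerting software. Two routes are therefore open on paper.

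- *Software run silently or retrospectively.* This needs EHR observations from a time when the alert was not visible. The protocol describes no such period in the four simultaneous-launch Trusts.
- *Concurrent patients who did not alert.* In the appendix table of algorithms, every listed Trust except ICHT has an infection question within its alert. Patients with similar observations but no alert may therefore exist, but they may differ from alerting patients on suspected infection itself. That factor bears on both treatment and mortality, so confounding would be strong.

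**Step 4: what does the ITS estimate?**
A control series removes changes that affect SoS and control patients alike. Where EHR and alert started together, any effect of the EHR specific to infection care stays in the estimate. The contrast in those four Trusts is therefore EHR plus alert.

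**The case against.** The strongest reply is that Section 7.2 never makes the time series purely secondary. It names ITS under the primary heading and says plans will vary with each Trust's implementation, so a Trust-by-Trust ITS in the appendix could be that principle carried out. The appendix also speaks of a primary outcome and does not call the ITS the primary analysis. This has force, and only the controlled multilevel version in SoS-coded patients is expressly secondary. But that is the version, in that population, that the appendix applies to the primary outcome. Naming two approaches as primary without ranking them leaves the question open.

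Several stronger readings are tempting, and the documents do not support them:

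- *A reader might infer that the matched analysis cannot be run in five of six Trusts.* The text allows alerting software and does not exclude concurrent controls. The supportable statement concerns pre-alert controls matched on electronic vital signs.
- *A reader might see a contradiction between a multilevel model and separate Trust models.* Section 7.2 also speaks of clustering within wards or Trust sites, so a multilevel model within one Trust fits both.
- *A reader might attach a false-positive rate to the separate Trust models, or a precision gain to pooling.* The impact study sets no significance level and no rule that one positive Trust counts as success, and the Trusts differ in algorithm and implementation.
- *A reader might hold that a pooled estimate is required.* Objective 4.1 seeks the most effective alert, which calls for Trust- or algorithm-specific effects.
- *A reader might treat the Welsh Trust as a pure comparison series.* The appendix defines the intervention to include changes in screening programmes, so its role is open.

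The protocol also openly admits confounding by EHR introduction and offers the control series in response. That is fair, but the control series deals only with shared effects.

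**Conclusion.** The concern holds. The protocol does not identify one primary analysis of its primary endpoint. The detailed plan develops the method and population that Section 7.2 calls secondary, and leaves the cohort comparison listed first as primary without a detailed plan. Since Section 10 places the detailed plans in the appendix, this is a conflict within one document and not a detail deferred elsewhere.

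On size: pre-alert controls matched on EHR vital signs appear available in 1 of 6 Trusts. This is an inference. It assumes that alert and EHR went live together in the four Trusts, as the appendix indicates without giving dates; that administrative data contain no vital signs; and that the Welsh Trust has no electronic observations. A gap between EHR launch and alert activation at any Trust would raise the count. No error rate or loss of precision can be derived from what the protocol states.

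**What to change.** In Sections 7.2 and 10 and in the appendix:

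1. Name the controlled ITS on 30-day in-hospital mortality in SoS-coded patients as the single primary analysis.
2. Make the matched or propensity analysis of alerting encounters a supporting analysis, restricted to Trusts with EHR data from before the alert (apparently ICHT only). If concurrent or software-identified controls are used elsewhere, say so and state the confounding risk.
3. State that in the four simultaneous-launch Trusts the ITS estimates the effect of EHR plus alert, because the control series removes only effects shared with control patients.
4. Keep the Trust-specific estimates. Say whether a pooled or multilevel summary will accompany them, and what part the Welsh Trust plays; both are the sponsor's choice.

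The cost is protocol wording; no new data are needed. The downside is a narrower claim for four Trusts. The primary analysis would also adjust for the case-mix factors that the appendix lists (age, sex, comorbidities, ethnicity) and season, and not for vital signs.

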8. PARTICIPANT IDENTIFICATION

WS2 – Participants, Inclusion and Exclusion Criteria

Study Participants

Patients aged over 18 attending the Emergency Departments and admitted as inpatients who are included in the scope of the alert in each trust.

From the hospital population we will identify patients aged between 18 and 110 who attend the Trust and lie within the scope of the alert. The scope of the alert will vary between Trusts, for example at ICHNT patients who are attend maternity wards and outpatient clinics are not currently included in the alert scope.

Inclusion Criteria

Patients who, on discharge or death, have an ICD-10 code included in the list of codes identified as Suspicion of Sepsis used in the Sepsis Insight Dashboard [www.sos-insights.co.uk]; Patients who 'alerted' - this is a binary indicator within electronic health records, this will depend on system the Trust uses to identify patients at risk of sepsis and/or deterioration related to sepsis. In order to carry out sensitivity analysis we will extract clinical information for patients with an ICD-10 code related to a condition as identified as being appropriate to the local health economy.

Exclusion Criteria

There are no pre-registration evaluations, no specific inclusion and exclusion criteria are there is no withdrawal from the study.

WS3 – Participants, Inclusion and Exclusion Criteria

Study Participants

Participants will include hospital healthcare professionals and patients/carers in the UK. The sample size will depend on saturation³³⁻³⁴, i.e. no new themes are identified in data from later interviews/focus groups, however it is estimated that around 25 healthcare professionals and 20 patients/carers will participate.

Analysis of data from the interviews and the focus groups will occur concurrently to data collection, where possible, to inform future sampling and data collection.

Inclusion Criteria

- Participant is willing and able to give informed consent for participation in the study.
- Any gender aged 18 years or above (no upper age limit).
- Fluent in English (or able to participate in an interview with other measures in place, e.g. interpreter).
- For clinicians: Currently working as a healthcare professional (e.g. doctor, nurse) in an NHS hospital trust.
- For patients/carers: Member of the public who has previously been diagnosed with sepsis and treated in hospital or carer/relative of someone who has previously had sepsis.

Exclusion Criteria

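### In the section 7.2 secondary analysis, stroke/trauma mortality is both the control series and the specificity check, so it gives no independent test of the control

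*Protocol*

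**What the plan says.** Under Sensitivity analysis, Protocol section 7.2 first treats stroke/trauma as a negative-control outcome: "We will consider mortality following an A&E attendance for stroke and/or trauma as an unrelated outcome in a sensitivity analysis". The purpose is explicit: "This will enable an assessment of the specificity of effect". So is the scope: "This will be included in primary and secondary analysis". The next sentence gives the same conditions a second role: "These conditions will be included as controls in controlled interrupted time series". The secondary analysis in section 7.2 is a controlled multilevel interrupted time series of mortality in SoS patients, so the two roles meet there.

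The case for these conditions is expert expectation, with a concession: "Although these patients may trigger an alert, we would not expect their treatment to be different after the introduction of the alert".

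Other places that bear on the point:

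- **Section 7.2, Primary analysis.** The comparator is a cohort clinically similar to the alerting patients, not stroke/trauma.
- **Section 8, WS2 inclusion criteria.** "In order to carry out sensitivity analysis we will extract clinical information for patients with an ICD-10 code related to a condition", in the singular, chosen to suit the local health economy.
- **Section 10.** Refers to the appendix for the detailed statistical plans.
- **Appendix, second plan (impact of a digital sepsis alert).** The control is falls in the opening cohort description and in 2.2 Participants, but gastrointestinal bleeding in 1.1 Background/rationale and Table 1. No negative-control outcome is named.

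**The concern.** The two roles read the same observation in opposite ways. For a negative-control outcome, a step at go-live is a warning that something other than the intended effect is at work. For a control series, a step at go-live is the shared shock that the design exists to remove. Such a shock is likely here: the appendix says that, except at one Trust, alerts arrived together with the electronic health record, and names this as a confounder.

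Section 7.2 gives no rule for telling the two readings apart, and one series cannot supply one. The controlled estimate relies on two assumptions: the alert does not touch the control condition, and the control shares the concurrent shocks of SoS patients. If stroke/trauma is the control, looking at stroke/trauma again does not test either assumption independently. What is at stake is a specificity statement for the secondary analysis that rests on a term already inside the estimate it is meant to support.

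**Working it through.** **Inputs.** The roles come from section 7.2. The study period, 1 April 2010 to 31 March 2021 (appendix, second plan, 2.1), gives 11 × 12 = 132 monthly points. The documents give no variance, effect size or power for this analysis; the appendix leaves power to be determined afterwards. There is therefore no figure to reproduce, and every other number below is an assumption.

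**Algebra.** Let a be the alert effect on SoS mortality, b its spill-over into the control, and s_S and s_C the concurrent shocks in each series.

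- SoS step = a + s_S
- Control step = b + s_C
- Controlled contrast = (a − b) + (s_S − s_C)

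The contrast equals a if b = 0 and s_S = s_C. Two observed steps cannot identify four unknowns.

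**Illustration.** Two-series interrupted time series fitted by least squares, with level and slope terms for each series; alert after 84 of 132 months; residual SD 0.8; steps in percentage points; 1,000 runs per row.

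| True state | True a | Control's own step | Controlled contrast |
|---|---|---|---|
| Shared shock −1 | −1 | −0.99 | −1.01 |
| Spill-over −1 | −2 | −1.00 | −1.00 |
| Shared shock −1 | 0 | −0.99 | −0.01 |
| Spill-over −1 | −1 | −0.99 | −0.01 |
| No shock, no spill-over | −1 | 0.01 | −0.99 |
| Shock to SoS patients only, −1 | 0 | 0.00 | −1.01 |

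Read in pairs, each two rows give the same control step and the same contrast, apart from simulation error, from different true effects. In the first two pairs, spill-over and a shared shock cannot be told apart. In the last pair the control is flat, so the check passes, yet one of the two estimates is wholly spurious.

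A shift peculiar to the control does the same on the ratio scale. If control mortality rises 10% for its own reasons and the alert does nothing, the controlled ratio is 1/1.10 = 0.91.

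**A second condition.** With stroke/trauma as the outcome and another unaffected condition as the control, a shared shock of −1 gave a contrast of 0.00 (rejected in 5% of runs), and spill-over of −1 into stroke/trauma gave −1.01 (rejected in 71%). The two explanations then separate.

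**Power of that test.** Assume a standard error of 0.06 per series on the log scale, independence, and a two-sided 5% test. The difference has standard error √2 × 0.06 = 0.085.

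- Shift of 0.20: z = 0.20/0.085 = 2.36; power = Φ(2.36 − 1.96) = 65%.
- Shift of 10%: ln 1.10 = 0.095; z = 0.095/0.085 = 1.12; power = Φ(1.12 − 1.96) = about 20%.

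**The case against.** The strongest reply is that section 7.2 expresses one idea: a condition not expected to respond to the alert supports specificity, and in a controlled time series it does so by being the control. That is an ordinary design, and the appendix gives the same rationale for a control. This stands as a defence of the control. It does not make the control series evidence about its own validity.

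A reader might infer more than the documents support:

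- **That the check can show nothing.** Stroke/trauma contrasted with itself is zero by construction, but no section proposes that contrast. The control's own step and slope are estimated in the model. In the simulation a step of −1 in the control was detected in about 93% of runs. At the assumed standard error of 0.06, a step of 0.20 has z = 3.33 and power Φ(3.33 − 1.96) = about 92%. What is lost is the attribution of a change, not sight of it.
- **That specificity is never assessed.** In the primary analysis stroke/trauma is not the comparator, so it remains a separate check there.
- **That the whole plan is circular.** The appendix time series subtracts falls or gastrointestinal bleeding, not stroke/trauma.
- **That the negative correlation between the control's step and the controlled estimate is itself a fault.** With equal precision it is −1/√2 = −0.71, but that holds for any difference and the term subtracted in it.

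It is also fair to say that a falsification model is often left to an analysis plan. Here, however, the protocol itself fixes the check and assigns it to the control series.

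**Conclusion.** The point holds for the controlled time series of the section 7.2 secondary analysis. There, one series is both the control and the evidence of specificity. A change in it at go-live cannot be attributed to spill-over, a control-specific shift or a shared shock, and a shock confined to SoS patients is missed. The double role and the algebra rest on the text alone. The sizes rest on assumed inputs: in the simulation, identical output arose from true effects of −1 and −2, of 0 and −1, and of −1 and 0 percentage points.

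The primary analysis is not affected. The appendix plan avoids the circularity but names two different controls of its own and no negative-control outcome, so the protocol nowhere sets out an independent test of the control. This is worth correcting, but it does not invalidate the study's main estimate.

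**What to change.** 1. Name one condition as the control in the controlled time series, and reconcile section 7.2 (stroke/trauma) with the appendix (falls in the cohort description and 2.2; gastrointestinal bleeding in 1.1 and Table 1).
2. Keep a different condition, already named in the protocol, as the negative-control outcome. The least editing would be to delete the section 7.2 sentence that makes stroke/trauma the control, and leave stroke/trauma in its first role.
3. Run the negative-control condition through the same controlled model in place of SoS patients. Report its step and slope with confidence intervals, next to the control's own step and slope.
4. State the reading in advance: a non-zero step or slope is evidence against parallel change; a null result is not proof of it. A shock confined to SoS patients, or equal spill-over into both conditions, would still go unseen.

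**Cost.** Some wording and one extra model per Trust. The extract may need a small addition, because section 8 speaks of a single condition and the appendix cohort is limited to SoS or falls codes. Power is limited (about 65% and 20% in the two cases worked above), so the interval matters more than the p-value.
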